12.1.9 Sensitivity Efficacy Analyses

Sensitivity analyses for absolute change in lesion count

The first sensitivity analysis for absolute change in lesion count use a repeated measures ANCOVA, with treatment, analysis center, and visit (ie, Week 4, Week 8) as independent factors and a covariate of baseline lesion count. In this analysis, data from all post-baseline visits will be included with no imputation for missing data.

The second sensitivity analysis will use the model based multiple imputation method to impute missing data for the absolute change in lesion counts at Week 12. Although the full details will be presented in the Statistical Analysis Plan (SAP), the multiple imputation will involve 4 principal tasks:

1. Calculate the number of missing values (nmiss) for absolute change in lesion count.
2. Missing values will be filled in ‘5 x nmiss’ times to generate ‘5 x nmiss’ complete data sets. The imputation model used will be an ANCOVA with factors of treatment group and analysis center, and a covariate of baseline lesion count (ie, the imputation model will be the same as the analysis model). Appropriate modifications will be made should the analysis be based on a non-parameteric method.
3. Each complete data set will be analyzed with an ANCOVA with factors of treatment group, and analysis center, and a covariate of baseline lesion count.
4. Results from these analyses will be combined into a single inference.

Sensitivity analyses for EGSS

The first sensitivity analysis for the dichotomized EGSS success will use a repeated measures logistic regression model (generalized estimating equations), with dichotomized EGSS success as the dependent variable and treatment, analysis center, and visit (ie, Week 4, Week 8) as independent factors. In this analysis, data from all post-baseline visits will be included with no imputation for missing data.

The second sensitivity analysis will use the model based multiple imputation method to impute missing data for the dichotomized EGSS data. Although the full details will be presented in the SAP, the multiple imputation will involve 4 principal tasks:

1. Calculate the number of missing values (nmiss) for absolute change in lesion count.
2. Missing values will be filled in ‘5 x nmiss’ times to generate ‘5 x nmiss’ complete data sets. The imputation model used logistic regression with factors of treatment group and analysis center (ie, the imputation model will be the same as the analysis model).
3. Each complete data set will be analyzed with a logistic regression a factors of treatment group and analysis center.
4. Results from these analyses will be combined into a single inference.

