The safety population will be comprised of all randomized subjects who are presumed to have used the study medication at least once and who provide at least one post-baseline evaluation. A per-protocol (PP) analysis will also be conducted. Subjects will be eligible for the PP analysis if they complete the 12-week evaluation without noteworthy study protocol violations (i.e., any Subject or investigator activity that could have possibly interfered with the therapeutic administration of the treatment or the precise evaluation of treatment efficacy). The PP population will include subjects in the ITT population who do not meet any of the following criteria:

- Failed any of the inclusion/exclusion criteria;
- Have taken any interfering concomitant medications;
- Did not attend the Week 12 visit, with the exception of a discontinuation from the study due to an adverse event related to study treatment or documented lack of treatment effect;
- Missed both the week 4 and week 8 visits;
- Have not been compliant with the dosing regimen (i.e. Subjects may not miss more than five consecutive days of dosing and must take 80-120% of expected doses. The number of expected doses will be determined for each subjects based on the length of their participation in the study);
- Out of visit window at the 12-week visit

Prior to breaking the blind, other additional criteria may be added to the list to accommodate for unforeseen events that occurred during the conduct of the trial that result in noteworthy study protocol violations.

Approximately eight hundred (800) subjects will be randomized to the following treatment groups:

- 400 Subjects to IDP-121 Lotion, once-daily application
- 400 Subjects to IDP-121 Vehicle Lotion, once-daily application

Efficacy:

Primary:

Co-primary efficacy analyses of the absolute change in inflammatory and in non-inflammatory lesions will be conducted on the ITT population. The pre-specified time point will be Week 12. Descriptive statistics will be presented by treatment group for inflammatory and for non-inflammatory lesions as well as the absolute change in inflammatory and in non-inflammatory lesions. All of the testing relating to the analysis of inflammatory and non-inflammatory lesions will use the methods introduced in Section 12.

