7.1 Overall Study Design and Plan: Description

This is a multicenter, randomized, double-blind, parallel-group study designed to assess the safety, efficacy and tolerability of IDP-121 Lotion in comparison with its vehicle. To be eligible for the study, subjects must be at least 9 years of age and older and have a clinical diagnosis of moderate to severe acne vulgaris (a score of 3 or 4 [moderate to severe] on the EGSS scale).

Approximately 800 subjects will be enrolled into this study and randomized into one (1) of two (2) treatment groups: 400 subjects in the IDP-121 Lotion, once daily application group, Version 4, 7 October 2016

CONFIDENTIAL

and 400 subjects in the IDP-121 Lotion Vehicle, once daily application group. Subjects will be enrolled at a minimum of 32 and maximum of 50 independent study centers. The duration of treatment will be 12 weeks. Subjects will be evaluated at Screening, Baseline and at subsequent follow-up visits (Weeks 4, 8, and 12).

An interactive web based response system (IWRS) will be employed to facilitate randomization of study patients. Treatment assignments and study drug kit numbers will be generated centrally by the IWR system. At each clinical site, subject numbers will be assigned consecutively at the screening visit starting with 001.

The assigned study drug will be applied topically to the face once daily for 12 weeks (up to week 12 visit). The initial application will be made at the investigational center as per instruction from the study coordinator or designee. The subjects will be instructed to avoid exposure to direct sunlight to prevent sunburn. Subjects will apply their daily treatments at home as explained by the study coordinator or designee at each investigational center. During post-baseline study visits (Weeks 4, 8 and 12) the subjects will be asked to return their used tubes of study drug and will be dispensed new tubes of study drug (only Weeks 4 and 8; Week 12 will be final visit). During the study, each subject will only be permitted to use approved non-medicated cleansers, moisturizers and sunscreens.

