The primary method of handling missing efficacy data will be based on estimation using the method of Markov Chain Monte Carlo (MCMC) imputation. This method provides robust estimation when the pattern of missingness is arbitrary. Additionally, the estimation will be done for each treatment group separately so that the pattern of missingness for one group does not influence the estimation of missing data for another group. Groups of complete datasets following the estimation will be concatenated to form analysis datasets for the comparative analyses and subsequent imputation result inference with SAS PROC MIANALYZE. Descriptive statistics will also be derived from the multiply imputed datasets.

Additionally, a model-based multiple imputation process will be used as a sensitivity analysis to the MCMC imputation. Finally, the absolute change in lesion count will be analyzed using a repeated measures ANCOVA for lesion count data or a repeated measures logistic regression model (generalized estimating equations) for the dichotomized EGSS.

A statistical analysis plan (SAP), describing all statistical analyses will be provided as a separate document. The SAP will be finalized prior to unblinding of the study treatments.

Evaluations and Analyses

Inflammatory lesions and non-inflammatory lesions will be recorded for each subject at Baseline and at Weeks 4, 8, and 12. The absolute and percent change from baseline of inflammatory lesions and non-inflammatory lesions will be derived for each subject at Weeks 4, 8, and 12.

The EGSS will be recorded for each Subject. The EGSS will be dichotomized into “success” and “failure” at Week 4, 8 and 12 with a subject considered a success for those visits if the Global Severity Score is at least 2 grades less than baseline and are Clear or Almost Clear. An additional assessment of subjects who have achieved 2 grade improvement will be also be conducted as a secondary efficacy variable.

The subject will be asked at Baseline and Week 12 to assess how oily their skin has been in the past week.

All assessments will be conducted for both ITT and PP.

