12.1.1 Primary Efficacy

There are three co-primary efficacy endpoints:

- Absolute change in inflammatory lesion count from baseline to Week 12
- Absolute change in non-inflammatory lesion count from baseline to Week 12
- Proportion of subjects who have a least a 2 grade reduction at Week 12 from baseline in the Evaluator's Global Severity Score and were Clear or Almost Clear

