12.1.5 Statistical Hypothesis Testing and Control of Multiplicity

Statistical hypothesis testing for lesion count analyses will use the statistical model introduced in Section 12.1.3 and employs the methods of Section regarding missing values. The analysis of the dichotomized Evaluator's Global Severity Score will be based on the logistic regression test stratified by analysis center and employs the methods of Section 12.1.7 regarding missing values.

The overall Type I error will be controlled by requiring the co-primary efficacy endpoints of each group to be statistically significant. Specifically, failure of any one of the primary efficacy endpoints will invalidate the statistical significance of the secondary efficacy endpoints.

The following stepwise process will be conducted for testing the secondary efficacy endpoints in order to control for multiplicity. These tests will be performed for only the ITT population. The testing process will terminate whenever a statistical test for a step is not significant. All subsequent tests for the remaining steps will be considered not significant. The order of testing is:

Step Number	Secondary Endpoint
1	Percent change in non-inflammatory lesion count from baseline to Week 12
2	Percent change in inflammatory lesion count from baseline to Week 12

The following stepwise process will be conducted for testing the supportive efficacy endpoints in order to control for multiplicity. These tests will be performed for only the ITT population. In order to control for multiplicity failure of any one of the secondary efficacy endpoints will invalidate the statistical significance of the supportive efficacy endpoints. The testing process will terminate whenever a statistical test for a step is not significant. All subsequent tests for the remaining steps will be considered not significant. The order of testing is:

Step Number	Supportive Endpoint
1	Percent change in non-inflammatory lesion count from baseline to Week 8
2	Percent change in inflammatory lesion count from baseline to Week 8
3	Percent change in non-inflammatory lesion count from baseline to Week 4
4	Percent change in inflammatory lesion count from baseline to Week 4
5	Proportion of subjects who have at least a 2 grade reduction at Week 12 from

	baseline in the Evaluator's Global Severity Score
6	Proportion of subjects who have at least a 2 grade reduction at Week 8 from baseline in the Evaluator's Global Severity Score

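### The repeated-measures sensitivity models have no treatment-by-visit term and no Week 12 contrast, so they estimate a visit average rather than the Week 12 co-primary effect

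*Combined protocol and SAP*

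**What the plan says.** Section 12.1.1 defines all three co-primary endpoints at Week 12, for example "Absolute change in inflammatory lesion count from baseline to Week 12". The Synopsis, under the primary efficacy analysis, says "The pre-specified time point will be Week 12".

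Section 12.1.9 gives two sensitivity analyses for each endpoint type. The second is model-based multiple imputation. The first is a repeated-measures model:

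- **Lesion counts:** an ANCOVA "with treatment, analysis center, and visit (ie, Week 4, Week 8) as independent factors and a covariate of baseline lesion count".
- **EGSS success:** a GEE logistic model with success "as the dependent variable and treatment, analysis center, and visit (ie, Week 4, Week 8) as independent factors".

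For both, "data from all post-baseline visits will be included with no imputation for missing data". Section 7.1 gives the post-baseline schedule as "subsequent follow-up visits (Weeks 4, 8, and 12"), so Week 12 data enter both models. The Synopsis and the opening of Section 12 mention the same models but add no interaction, no time point and no covariance structure.

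**The concern.** A model with one treatment term, visit as a main effect and data from three visits fits a single treatment effect common to all visits. That is a precision-weighted average of the Week 4, Week 8 and Week 12 differences. It is the Week 12 effect only if the effect does not change over the 12 weeks.

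This matters because these are the only sensitivity analyses that avoid imputation, so they are the natural check on the multiply imputed Week 12 result. As written, they change two things at once: how missing data are handled and which quantity is estimated. A gap from the primary result could be due to visit averaging rather than missing data. Agreement could not be read as robustness to missing data alone.

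There is also a smaller inconsistency. The bracketed visit list names only Weeks 4 and 8, while the sentence after it brings in every post-baseline visit. This is most likely a slip.

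**Working it through.** **Inputs from the plan (Section 12.8.2).** 400 per arm; lesion changes 6.5 vs 3.5, SD 11.3; 17.8 vs 9.9, SD 24.7 (lesion types not named there); EGSS success 23% vs 14%; two-sided alpha 0.05.

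**The plan's own figures reproduce.** Power for means is Φ(δ/(σ√(2/n)) − 1.96).

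- 3.0/(11.3 × √(2/400)) = 3.0/0.799 = 3.75, so power is 96.4% (stated: at least 96%).
- 7.9/(24.7 × √(2/400)) = 7.9/1.747 = 4.52, so power is 99.5% (stated: greater than 99%).
- 23% vs 14% gives 90.8% (stated: approximately 90%).

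These Week 12 effects are what a Week 12 sensitivity analysis should target.

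**What the common coefficient estimates, lesion counts.** Let V be the covariance matrix of the outcome over Weeks 4, 8 and 12, and d the vector of visit-specific treatment differences. With one treatment term and complete data, the coefficient is w′d, where w = V⁻¹1/(1′V⁻¹1). The documents give neither d at Weeks 4 and 8 nor V, so the following profiles, SDs and correlations are assumptions.

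With equal SDs, compound symmetry gives weights 1/3, 1/3, 1/3. AR(1) with correlation 0.4 to 0.7 gives 0.385/0.231/0.385 to 0.435/0.130/0.435. Every profile below is linear over visits, so both structures give the same answer. For the first profile, (1/3 + 2/3 + 1)/3 = 0.667, and 0.667 × 3.0 = 2.0. The last column lets the SDs be 0.8, 0.9 and 1.0 of the Week 12 SD (compound symmetry or AR(1), correlation 0.4 to 0.7), which shifts weight to Week 4.

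| Effect at Weeks 4, 8, 12 as a share of Week 12 | Equal SDs: share | Equal SDs: lesions (Week 12 = 3.0) | Rising SDs: share |
|---|---|---|---|
| 1/3, 2/3, 1 | 67% | 2.0 | 46–59% |
| 0.5, 0.75, 1 | 75% | 2.25 | 59–69% |
| 0.8, 0.9, 1 | 90% | 2.7 | 84–88% |
| 1, 1, 1 | 100% | 3.0 | 100% |
| 1.1, 1.05, 1 | 105% | 3.15 | 106–108% |

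The largest gap in the table is (1 − 0.456) × 3.0 ≈ 1.6 lesions. The early-effect profile has the opposite sign: 3.0 − 3.15 = −0.15 with equal SDs.

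**EGSS.** The Week 12 odds ratio is (0.23/0.77)/(0.14/0.86) = 1.83. Assume vehicle success of 3% and 8% at Weeks 4 and 8, and apply the profiles to the log odds ratio. Solving the population GEE equations with three visit intercepts and one treatment log odds ratio gives:

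| Profile | Independence | Exchangeable 0.3 | Exchangeable 0.5 |
|---|---|---|---|
| 1/3, 2/3, 1 | 1.64 | 1.71 | 1.79 |
| 0.5, 0.75, 1 | 1.68 | 1.74 | 1.80 |
| 0.8, 0.9, 1 | 1.77 | 1.79 | 1.82 |
| constant | 1.83 | 1.83 | 1.83 |

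The gap is milder here because the early visits have few successes and so carry little weight.

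**A scale for comparison.** Suppose 10% of subjects were missing at Week 12 (assumed) and had no improvement. The 3.0 difference would move by 0.10 × (6.5 − 3.5) = 0.30 if this applied to both arms, or by 0.10 × 6.5 = 0.65 if only to the active arm. That is a deliberately harsh scenario, and the averaging gap can still be as large.

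**The case against.** The strongest objection is that the protocol is not the final word. Section 12 promises a SAP "describing all statistical analyses will be provided as a separate document", and that SAP may contain the interaction. Its text is not in the material reviewed, so what is shown is that the protocol's description omits the term. That caveat stands. However, within Section 12.1.9 the explicit deferral to the SAP attaches only to the imputation analyses. The repeated-measures models are stated as if complete, and elsewhere (Sections 12.1.4 and 12.1.7) the protocol writes out an interaction, treatment by analysis center, when it wants one.

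Second, an all-visits average can be a legitimate supportive quantity, and the protocol never says this model must estimate the Week 12 effect. That is true, but a result headed as a sensitivity analysis of a Week 12 endpoint is useful only if it addresses the same question.

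Third, Section 12.1.5 tests visits separately (for example "Percent change in non-inflammatory lesion count from baseline to Week 8"), but this does not show that effects differ over time, and those tests use percent change and two-grade reduction rather than the outcomes modelled here. This is fair: the separate tests show only that the plan does not rely on a constant effect.

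Fourth, the sizes rest on assumed profiles, and for EGSS some are negligible. This also stands, so the figures are illustrations and not estimates of bias.

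Finally, the visit list may be shorthand for two visit indicators with Week 12 as reference. That would explain the list, but without an interaction the treatment coefficient is still common to all visits.

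**Conclusion.** The concern holds. Followed as written, both repeated-measures models estimate a visit-weighted treatment effect rather than the Week 12 effect that defines the co-primaries. The gap is zero if the effect is constant. Under the assumed profiles, the count coefficient runs from 46% to 108% of the Week 12 effect, and the EGSS odds ratio for growing effects is 1.64 to 1.82 against 1.83. Neither size nor direction can be fixed from the documents, because they give no Week 4 or Week 8 effects, SDs or correlations.

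The reach is limited. The co-primary tests, stated power and multiplicity rules do not depend on these models, and the imputation-based sensitivity analysis still addresses Week 12 (stated explicitly for counts). What is weakened is the only non-imputation check on the primary results. It should be corrected, subject to whatever the separate SAP already says.

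**What to change.** In Section 12.1.9, and in the SAP before unblinding:

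1. Name Weeks 4, 8 and 12 as the visit levels in both models.
2. Add treatment-by-visit to the repeated-measures ANCOVA and to the GEE.
3. State that the sensitivity result is the Week 12 treatment contrast: the adjusted mean difference for counts and the odds ratio for EGSS success.

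A baseline-by-visit term and an unstructured covariance for the counts are sensible but optional; the covariance and the GEE working correlation should in any case be stated. The cost is one line of wording and model code per endpoint type, with no new data and no effect on sample size or the testing order.

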12.1.10 Subgroup Analyses

Subset analyses will be conducted for the ITT populations for the subgroups baseline global severity, gender, age, ethnicity, race, and geographic location. Age will be dichotomized to less than the median age of subjects and greater than or equal to the median age of subjects. An additional analysis will be include with categories of less than 18, 18 to less than the median age and greater than or equal to the median age. Geographic region will be dichotomized to US and outside US (OUS). Subset analyses will be conducted on the variables absolute change from baseline in inflammatory lesions and non-inflammatory lesions at Week 12 as well as the dichotomized global severity score at Week 12. These analyses will contain only descriptive statistics.

12.2 Assessment of Safety

Safety will be evaluated by tabulations of adverse events (AEs), Cutaneous Safety Evaluation, and Tolerability Evaluations. Cutaneous Safety Evaluation scores (erythema, scaling, and hypo/hyper-pigmentation) and Tolerability (itching, burning, and stinging) will be presented with descriptive statistics at Baseline and at Weeks 4, 8, and 12 for each treatment group. Frequencies and percentages for each outcome category will be included in these statistics. Mean values will be presented graphically by week and treatment group.

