Currently, therapeutic treatment of acne is directed against 3 principal pathogenic factors of the disease, including the bacterial colonization of follicles, the hypersecretion of the sebaceous gland, and intrafollicular hypercornification that induces follicular obstruction. Effective treatment directed against the colonization of bacteria (*P. acnes*) in follicles has made use of anti-infectives such as topical benzoyl peroxide (2.5%-10%), clindamycin, and erythromycin and systemic tetracyclines; however, known disadvantages to this treatment modality include irritation and limited use due to pathogen resistance [2-5]. Effective treatment directed towards inhibiting sebaceous gland activity has included oral corticosteroids, spironolactone, and isotretinoin in addition to anti-androgens (eg, cyproterone acetate). Known disadvantages to this treatment modality include being limited to use in females (anti-androgens), and limited to short term use for safety (oral corticosteroids). Finally, effective treatment directed against intrafollicular hypercornification has made use of retinoids such as oral isotretinoin and topical tretinoin or isotretinoin to regulate the intrafollicular keratinization process, inhibiting follicular hyperkeratinization and follicular obstruction [6]. In general, the known usefulness of oral retinoids (ie, oral isotretinoin) is limited by their side effects, which range from relatively minor effects (eg, dryness of mucosa and skin, skin irritation, and skin scaling) to major toxicity syndromes (reversible hair loss, bone toxicity and teratogenicity) and may include varying degrees of symptoms associated with hypervitaminosis A syndrome [2, 7, 8]. Likewise, the efficacy of topical retinoids such as tretinoin or isotretinoin may be limited by the known side effects, which include significant erythema, dryness, peeling, scaling, and irritation [9].

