Photographs (select sites only)		X			X
Cutaneous Safety Evaluation		X	X	X	X
Tolerability Evaluation		X	X	X	X
Randomization in IWRS (obtain kit #)		X	X	X	
Administer Subject Instructions (Appendix 17.1)		X			
Dispense Study Drug ⁵		X	X	X	
Weigh Study Drug to the nearest 0.1gram		X	X	X	X
Study Drug applied at investigational center		X			
Study Drug Collected			X	X	X
Subject Diary Calendar dispensed		X	X	X	
Subject Compliance Reviewed / Diary			X	X	X
Adverse Events	X	X	X	X	X
Concomitant Therapy and Prohibited Therapies Review	X	X	X	X	X
End of Study					X

¹ If no washout is needed, Visits 1 and 2 may occur on the same day. If a washout is needed, Visit 2 must occur after the appropriate washout period.

² All visit dates are in reference to baseline, e.g., Visit 4 occurs 8 weeks +/- 3 days after baseline visit.

³ All Week 12 procedures should be completed for all subjects who terminate early.

⁴ The Week 2 SSA will be sent home with the subject during the baseline visit (Visit 2) with instructions to complete it at two weeks and return it at the Week 4 visit. The site should call the subject at Week 2 to remind them to take the Week 2 SSA.

⁵ Dispense one tube of test material at the Baseline, Week 4 and Week 8 visits.

8 Selection and Withdrawal of Subjects

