11.2.1 Evaluator's Global Severity Score (EGSS)

The Evaluator's Global Severity Score will be a static assessment that is independent of the baseline score. The investigator will make the assessment without referring to the baseline value. Every effort should be made for the same evaluator to perform each study assessment for the same study subject, for consistency in evaluations.

Subjects are eligible if they have acne with a global severity of a 3 (moderate) or a 4 (severe) on the EGSS at the baseline visit. The following scores will be used to describe the severity grade and subsequent score:

Table 4. Evaluator's Global Severity Score

Score	Grade	Description
0	Clear	Normal, clear skin with no evidence of acne vulgaris
1	Almost Clear	Rare non-inflammatory lesions present, with rare non-inflamed papules (papules must be resolving and may be hyperpigmented, though not pink-red)
2	Mild	Some non-inflammatory lesions are present, with few inflammatory lesions (papules/pustules only; no nodulocystic lesions)
3	Moderate	Non-inflammatory lesions predominate, with multiple inflammatory lesions evident: several to many comedones and papules/pustules, and there may or may not be one nodulocystic lesion
4	Severe	Inflammatory lesions are more apparent, many comedones and papules/pustules, there may or may not be up to 2 nodulocystic lesions

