11.3.1 Cutaneous Safety Evaluations

Cutaneous safety will be evaluated through assessment of scaling, erythema, hypo-pigmentation and hyper-pigmentation at the drug-application site at the time of the visit. Cutaneous tolerability will be evaluated through assessment of selected local signs and symptoms at the drug-application site: itching, burning and stinging at the time of the visit.

Cutaneous tolerability signs and symptoms that result in the subject's requiring a concomitant therapy, interruption of treatment, or discontinuation from the study, will be reported as an AE.

(Note: To be assessed by the evaluator at the time of the study visit.)

Scaling:

0 – None	No scaling
1 – Mild	Barely perceptible, fine scales present on limited areas of the face
2 – Moderate	Fine scale generalized to all areas of the face
3 – Severe	Scaling and peeling of skin over all areas of the face

Erythema:

0 – None	No evidence of erythema present
1 – Mild	Slight pink coloration
2 – Moderate	Definite redness
3 – Severe	Marked erythema, bright red to dusky dark red in color

Hypo-pigmentation:

0 – None	No evidence
1 – Mild	Slight, barely perceptible
2 – Moderate	Definite, evident
3 – Severe	Marked, prominent

Hyper-pigmentation:

0 – None	No evidence
1 – Mild	Slight, barely perceptible
2 – Moderate	Definite, evident
3 – Severe	Marked, prominent

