11.4.2 Documenting Adverse Experiences

It is the responsibility of the investigator to document all AEs that occur during the course of the study. The AEs should be documented as a single medical diagnosis. When this is not possible, the AE should be documented in terms of signs and/or symptoms observed by the investigator or reported by the subject at each study visit. Each AE which appears to be independent of any prior event will be reported separately.

All AEs occurring after the subject signs the informed consent through the last study visit must be reported, regardless of whether or not the AEs are considered drug-related. All AEs, whether in response to a query, observed by the study site personnel, or reported spontaneously by the subject, will be recorded. Any AEs deemed related to treatment reported or observed at the final study/treatment visit will be followed until stabilization or resolution (or up to 30 days after final study visit).

At each visit during the study, the subject will be assessed for the occurrence of new and ongoing AEs. Cutaneous tolerability signs and symptoms that result in the subject's requiring a concomitant therapy or discontinuation from the study will be reported as an AE. The following data will be collected on all AEs and recorded on the appropriate CRF:

- Event name (diagnosis preferred, if unknown, record the signs/symptoms)
- Onset date and end date
- Maximum intensity (severity)
- Seriousness
- Action taken regarding study drug
- Corrective treatment, if given

- Outcome

In addition, the investigator's assessment of causality will be recorded.

Vital sign abnormalities are to be recorded as AEs only if they are clinically significant (for example: are symptomatic, requiring corrective treatment, leading to discontinuation or fulfilling a seriousness criterion).

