12.2.2 Safety Laboratory Tests

Changes from baseline in safety laboratory values will be summarized with descriptive statistics at Week 12. Shift tables will be presented for changes in safety laboratory values. Normal ranges established by the central laboratory will be used to determine the shifts. A listing of all out-of-range laboratory test results at any assessment time point will also be provided. Determination of clinical significance for all out-of-range laboratory values will be made by each investigator and included in the listing. In addition, a listing of all clinically significant laboratory test results will be provided.

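### The seven cutaneous scores are summarised by scheduled visit only, with no worst post-baseline or shift summary and no rule for placing early-termination scores

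*Combined protocol and SAP*

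**What the plan says.** The Synopsis and Section 6 make tolerability part of the study objective. Section 11.3 defines seven scores, each graded 0 to 3. Scaling, erythema, hypo-pigmentation and hyper-pigmentation are graded by the evaluator. Itching, burning and stinging are reviewed with the subject.

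Section 12.2 says that these scores "will be presented with descriptive statistics at Baseline and at Weeks 4, 8, and 12 for each treatment group". Category frequencies are included, and "Mean values will be presented graphically by week and treatment group". The same section also names adverse event tabulations as part of the safety evaluation.

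For laboratory data, Section 12.2.2 goes further: "Shift tables will be presented for changes in safety laboratory values".

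On early leavers, a footnote to Table 1 states: "All Week 12 procedures should be completed for all subjects who terminate early". Those procedures include the cutaneous evaluations.

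Section 11.3.1 adds that tolerability signs and symptoms leading to concomitant therapy, "interruption of treatment, or discontinuation from the study, will be reported as an AE".

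**The concern.** The Introduction gives the reason these scores matter: "the efficacy of topical retinoids such as tretinoin or isotretinoin may be limited by the known side effects", and it goes on to list erythema, dryness, peeling, scaling and irritation. Yet these scores receive a thinner display than the laboratory values.

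A table of percentages at each visit answers how many subjects were affected on that day. It does not answer two questions that a tolerability objective raises: how many were affected at any time, and how many became worse than they were at entry. The second matters because the face is already diseased at Baseline, so a redness score after Baseline means little without the subject's own starting grade.

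There is also a question about leavers. A subject who stops because of irritation should have a last set of scores from the early-termination visit, but nothing says which column those scores enter. If they enter none, the later columns lean towards subjects who tolerated the lotion.

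**Working it through.** No figure in the plan bears on this point. The power figures in Section 12.8.2 concern efficacy, and no rate of irritation or dropout is given. The check is therefore a comparison of sections, followed by two illustrations on assumed rates.

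**1. What is planned for each kind of safety data**

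- Cutaneous scores (12.2): descriptive statistics and frequencies by visit, and graphs of means. No change from Baseline, shift, worst score or number assessed per visit is named.
- Laboratory values (12.2.2): change from Baseline and shift tables.
- Vital signs (12.2.3): change from Baseline.
- Adverse events (12.2.1): each subject counted once at highest severity and once at greatest relationship, whatever the visit.

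**2. Where an early-termination score goes**

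- Section 12.8.6 gives windows for the scheduled visits only.
- Section 12.8.3 refers missing data to Section 12.1.8, which covers lesion counts and EGSS only.
- No other section assigns these scores to a visit. They may be left out, or they may be placed in Week 12 because they are collected as Week 12 procedures.

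**3. Ever affected, with nobody leaving**

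Assume that 3% are severe at each of the three post-baseline visits. If they are the same subjects each time, 3% were ever severe. If they are different subjects each time, 3 × 3% = 9% were. The by-visit table is the same in both cases.

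**4. Effect of leaving, if early-termination scores are left out of Week 12**

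Let p be the share ever at least moderately irritated, and q the share of those who leave before Week 12, with the same q in both arms. Assume that irritated subjects who stay are still irritated at Week 12, and that no other loss is informative. Then

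Week 12 percentage = p(1 − q) / (1 − pq),

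while a worst-score table shows p.

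Worked case, with p = 10% on active and 3% on vehicle, and q = 50%:

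- Active: 0.10 × 0.50 / (1 − 0.05) = 0.050 / 0.950 = 5.3%
- Vehicle: 0.03 × 0.50 / (1 − 0.015) = 0.015 / 0.985 = 1.5%
- Difference shown: 3.7 points from unrounded values, against a true 7.0

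| p, active vs vehicle | True difference (points) | Shown, q = 25% | q = 50% | q = 75% |
|---|---|---|---|---|
| 5% vs 2% | 3.0 | 2.3 | 1.6 | 0.8 |
| 10% vs 3% | 7.0 | 5.4 | 3.7 | 1.9 |
| 20% vs 5% | 15.0 | 12.0 | 8.5 | 4.6 |

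At q = 0 nothing is lost. If early-termination scores are placed in Week 12, most of the loss disappears, though an early score is then presented as a Week 12 score. The missing rule decides which case applies.

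**The case against.** The strongest reply is that irritation is not reported through these scores alone. A reader might infer from Section 12.2 that a subject driven out by irritation vanishes from the safety report. The documents do not support that. Such irritation is a reportable adverse event under Section 11.3.1, and Section 12.2.1 summarises events by highest severity, by relationship and with Fisher's exact test, without conditioning on attendance at Week 12. Section 12.2.1 also lists discontinued subjects, and Section 12.3 tabulates the reasons for leaving. This objection stands, and it limits the point to the score displays.

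It does not close the gap entirely. The special reporting rule needs a consequence such as treatment or discontinuation, so it does not by itself catch a severe score that the subject endures. It speaks of tolerability, which Section 11.3.1 describes as itching, burning and stinging. Its reach to erythema, scaling and pigmentation is unclear, although the general definition in Section 11.4.1 covers signs that worsen. Section 11.4.2 restates the rule as "concomitant therapy or discontinuation from the study will be reported as an AE" and omits interruption of treatment, so the two sections must be reconciled. Discontinuations are listed and their reasons tabulated, but no by-arm table of events leading to discontinuation is named.

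A second reply is that Section 12.2 states no denominator and early leavers are asked for Week 12 assessments, so loss of their scores is possible but not shown. That is right.

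A third concerns acne itself. A reader might infer from the Almost Clear grade of the EGSS ("papules must be resolving and may be hyperpigmented, though not pink-red") that redness or pigment change from acne invalidates the scores. Randomisation 1:1 against vehicle and Baseline scores tabulated by arm largely answer this between arms. What remains is that acne may clear more on active, so that acne-related redness falls more there and partly hides drug erythema. A worst-score table does not separate the two causes and would also count acne flares as worsening.

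Finally, Section 12 refers to a separate SAP. No separate SAP text is in the combined file, so some of this may be covered there.

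**Conclusion.** The point holds as a gap in how the seven scores are displayed. As written, the score tables cannot give the share of subjects ever affected or the share who worsened from their own baseline, and they may leave out the last scores of early leavers. The first two limits follow from the by-visit format and need no assumption about dropout. The third depends on a placement rule that the protocol does not state.

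The size cannot be computed from the documents. The figures above rest entirely on assumed rates, and those on leavers also assume that early-termination scores are excluded from Week 12. They show the possible direction and not an expected bias. It would go too far to conclude that the tolerability objective as a whole will be answered too favourably, because the adverse event and disposition outputs also answer it. The efficacy inference is not affected. This is an inexpensive improvement that is worth making.

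**What to change.** In Section 12.2, or in the SAP:

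- For each of the seven scores, add a table by arm of the shift from Baseline to the worst post-baseline score. Include early-termination scores, and unscheduled scores if any are collected; Table 1 schedules none.
- In the same table, give the percent worsening by at least 1 grade and the percent reaching grade 3, based on all dosed subjects with any post-baseline score.
- Show the number assessed at each visit in the by-visit tables and graphs.
- State how early-termination scores are assigned to visits.

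Sections 11.3.1 and 11.3.2 should also be reconciled. One places itching, burning and stinging at the time of the visit, the other as an average since the previous visit, and this decides what a worst score means.

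The cost is analysis wording and seven descriptive tables from scores the protocol already collects. The downside is that the reported irritation rates will look higher than the by-visit rates. The change does not claim to separate acne from drug effects; that still rests on the comparison with vehicle.
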